13.1.6.3. Urinalysis

Analytes that will be tested include: appearance, bilirubin, color, nitrite, occult blood, pH, protein, specific gravity, glucose, ketones, red blood cell (RBC), and WBC. If required, microscopic analysis of sediment will be performed and reported per occurrence.

13.2. Adverse and Serious Adverse Events

13.2.1. Definition of Adverse Events

13.2.1.1. Adverse Event (AE)

An AE is any untoward medical occurrence associated with the use of a drug in humans, whether or not considered drug related. It may be indicated by physical sign, symptom, clinically significant laboratory abnormalities, and/or disease temporally associated with a medical (investigational) treatment, procedure, or product, whether or not related to the medical (investigational treatment, procedure or product. This definition includes intercurrent illnesses or injuries, exacerbation of pre-existing conditions, or events occurring due to abuse or overdose.

Any condition that was pre-existing is not an adverse event unless there is a change in the nature, severity, or degree of the condition.

Clinical laboratory abnormalities are considered AEs when deemed clinically significant by the Investigator and/or lead to a change in the subject's functional status.

An AE does not include:

- Medical or surgical procedures (e.g., colonoscopy, biopsy). The medical condition that leads to the procedure is an AE.
- Social or convenience hospital admissions where an untoward medical occurrence did not occur.
- Day-to-day fluctuations of pre-existing disease or conditions present or detected at the start of the trial that do not worsen.
- The disease/disorder being studied or expected progression, signs, or symptoms of the disease/disorder being studied unless more severe than expected for the subject's condition.

All Investigators conducting investigative studies supported by Capricor must report both expected and unexpected SAEs to Capricor, or designee, and their individual Institutional Review Board (IRB) in compliance with their institutional policies. Please see Section 13.2.4 or further details on event reporting.

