DMD occurs in early childhood, with degeneration occurring progressively in the skeletal musculature and ultimately in the heart and respiratory muscles, resulting in premature death (Hendriksen et al., 2015). Progressive weakness and muscle atrophy caused by degenerating muscle fibers begins in the lower extremities and pelvis before spreading into the upper extremities. Other symptoms include loss of some reflexes, a waddling gait, frequent falls, difficulty when rising from a sitting or lying position or when climbing stairs, changes to overall posture, and impaired breathing. Many children precipitously lose the ability to run or jump. The atrophied muscles, in particular the calf muscles, and less commonly, muscles in the buttocks, shoulders, and arms, may be enlarged by an accumulation of fat and connective tissue, causing them to look larger and healthier than they actually are (“pseudohypertrophy”). Bone thinning and scoliosis are common. Ultimately, a wheelchair becomes necessary, in most cases between 12 to 15 years of age (Henricson et al., 2013).

[figure not shown]
As the disease progresses, the muscles in the diaphragm that assist in breathing and coughing become weaker. Affected individuals experience breathing difficulties, respiratory infections, and swallowing problems. Almost all DMD patients will develop cardiomyopathy (Aartsma-Rus et al., 2016). Pneumonia, compounded by cardiac involvement, is the most frequent cause of death, which typically occurs in the late teens or early 20s. However, improvements in multidisciplinary care, in particular respiratory care and various forms of assisted ventilation, have extended the life expectancy; numerous individuals with DMD now survive into their 30s, and some even into their 40s (Emery, 2002; Bushby et al., 2010; Bushby et al., 2010).

No pharmacologic or biological therapies proven to stop or reverse the progression of DMD have been approved in the US. Disease management consists primarily of preventive measures as well as active interventions to address the primary and secondary aspects of the disorder.

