13.2.1.2. Serious Adverse Event (SAE)

An AE is considered “serious” if, in the view of either the Investigator or Capricor, it results in any of the following outcomes:

- Death
- Life-threatening adverse event
- Inpatient hospitalization or prolongation of existing hospitalization
- Persistent or significant incapacity or substantial disruption of the ability to conduct normal life functions
- Congenital anomaly/birth defect

Important medical events that may not result in death, be life-threatening, or require hospitalization may be considered serious when, based upon appropriate medical judgment, they may jeopardize the subject and may require medical or surgical intervention to prevent one of the outcomes listed in this definition.

Examples of such medical events include bronchospasm requiring intensive treatment in an emergency room or at home, blood dyscrasias, or convulsions that do not result in inpatient hospitalization, or the development of drug dependency or drug abuse.

Complications that occur during a hospitalization are AEs. When the hospitalization is prolonged due to the complication or the complication fulfills any other serious criteria, the event is reported as an SAE. Hospitalization for elective treatment of a pre-existing condition that did not worsen from baseline is not considered an SAE.

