13.2.3. Recording Adverse Events

Investigators will monitor all subjects for AEs during the trial and establish a diagnosis for an event based on signs, symptoms, and/or other clinical information. It is important to distinguish that individual signs and symptoms of the event are not adverse events and should not be reported.

For each AE, the Investigator will evaluate the causality and severity, report the action taken and event outcome and disclose whether or not it caused the subject to discontinue trial participation.

The following severity scale will be used as a guideline to differentiate the severity of adverse events:

- **Mild (Grade 1)**: Transient or mild discomfort; no limitation in activity; no medical intervention/therapy required
- **Moderate (Grade 2)**: Mild to moderate limitation in activity – some assistance may be needed; no or minimal medical intervention/therapy required
- **Severe (Grade 3)**: Marked limitation in activity, some assistance usually required; medical intervention/therapy required and often requiring hospitalization or prolongation of hospitalization

- **Life-Threatening or Disabling (Grade 4):** Extreme limitation in activity, significant assistance required; significant medical intervention/therapy required; hospitalization, prolongation of hospitalization, or hospice care
- **Fatal (Grade 5)**

An AE that is assessed as severe should not be confused with an SAE. Severity is a category utilized for rating the intensity of an event. An event is described as “serious” when it meets one of the pre-defined outcomes noted in Section 13.2.1.2. Both an AE and SAE can be assessed as severe. However, an AE of severe intensity may not meet SAE definition requirements.

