6.3.10 Resource Utilization

No endpoint-specific displays will be produced.

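### The AE definition excludes expected DMD progression with no override for serious events and conflicts with neighbouring text, so sites may classify respiratory and cardiac admissions differently, and no remaining display counts those set aside

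*Protocol*

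**What the plan says.** Protocol 13.2.1.1 excludes from adverse events "The disease/disorder being studied or expected progression, signs, or symptoms of the disease/disorder being studied unless more severe than expected". The one exception reads in full "unless more severe than expected for the subject's condition". The same section counts intercurrent illnesses and exacerbations of existing conditions as AEs. It also treats a pre-existing condition as an AE once its character, severity or extent changes.

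Protocol 13.2.1.2 opens with "An AE is considered “serious” if" and lists outcomes that include "Inpatient hospitalization or prolongation of existing hospitalization". An elective admission for an existing condition that has not got worse is expressly not an SAE. The section does not mention an unplanned admission attributed to progression. Protocol 13.2.3 separates the two scales: "An AE that is assessed as severe should not be confused with an SAE".

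Protocol 5.1 describes heart and respiratory decline as the course of DMD: "Affected individuals experience breathing difficulties, respiratory infections, and swallowing problems".

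Hospitalization was also to be examined outside the AE system, as an exploratory resource-utilization endpoint (Protocol 7.2.3 and 14.5.3) and in an all-cause pharmacoeconomic analysis (Protocol Synopsis). For resource utilization, SAP 6.3.10 now says "No endpoint-specific displays will be produced". SAP 8 lists the endpoint as not analysed, Addendum 2.6 does not reinstate it, and Addendum 4 reports that the all-cause analysis was not completed.

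**The concern.** Serious adverse events are a primary safety endpoint (Protocol 7.2.1). Whether a respiratory or cardiac admission enters that endpoint can depend on whether the investigator regards it as expected for that boy's disease. No criterion is given for that judgment, and the only stated exception concerns severity, not seriousness. If treatment made respiratory or cardiac decline faster, a modest acceleration could be hard to tell from natural progression in a single subject.

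SAE status also triggers 24-hour reporting to the sponsor and review by the DSMB (Protocol 13.2.4). An admission set aside at the AE step misses both. A count of hospitalizations that ignored AE status would have been the natural cross-check, and none remains.

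**Working it through.** The documents give no hospitalization rate and plan no formal safety test (Protocol 14.4), so there is no figure of theirs to reproduce. The check is a trace through the text, followed by an illustration of scale.

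**1. Can an admission fall outside the SAE definition?** An SAE must first be an AE (13.2.1.2). Expected progression is not an AE unless it is unusually severe for the subject (13.2.1.1). Severity and seriousness are distinct (13.2.3), so the severity exception does not act as a seriousness exception. The instruction to report both expected and unexpected SAEs (13.2.1.1, 13.2.4) applies only once an event is an SAE. On this reading, an admission judged to be expected progression is not an SAE.

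**2. Does the same text point the other way?** Yes. A respiratory infection can be read as an intercurrent illness, and a cardiac deterioration as an exacerbation or a change in an existing condition. Section 13.2.1.2 rules out only the elective, unworsened admission, and 13.2.1.1 rules out social or convenience admissions. An unplanned admission for worsening is in neither group. Both readings are open, and the documents do not say which prevails.

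**3. What would still count an admission that was set aside?**

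- Resource utilization: it covered admissions for orthopedic injury or surgery and pulmonary infection, not cardiac ones; dropped (SAP 6.3.10, SAP 8, Addendum 2.6).
- All-cause hospitalizations: not completed (Addendum 4).
- AE tables: built from TEAEs (SAP 7.1, Addendum 3.1), so they inherit the AE definition.
- All-cause mortality: counts deaths only.
- Respiratory decompensation, hypersensitivity and immune sensitization: separately defined and adjudicated, but tied to the infusion or to an antibody response. The first covers only the 2 hours after dosing.
- Ventilatory-support and oxygen listings (SAP 5.4), FVC, PEF and IFR (SAP 6.3.7), cardiac MRI (SAP 6.3.8) and cardiac medications (Addendum 3.2): these may show consequences but do not count admissions.

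The Schedule of Assessments (Protocol Table 3) has no row for hospitalizations. AE reporting is therefore the main visible route of capture, although the case report forms are not among the documents.

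**4. Scale.** Inputs: 20 randomized (Protocol 14.2), 1:1 (Protocol 9.4), so about 10 per arm. One subject is 1/10 = 10 percentage points. Exact (Clopper-Pearson) 95% intervals are 0 to 30.8% for 0/10 and 0.3 to 44.5% for 1/10.

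Assume a 12-month admission risk p per subject and a share f of admissions set aside as progression. The chance that an arm of 10 shows at least one is 1 − (1 − p(1 − f))^10:

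| | p = 5% | p = 10% | p = 20% |
|---|---|---|---|
| f = 0 (all counted) | 40.1% | 65.1% | 89.3% |
| f = 0.5 | 22.4% | 40.1% | 65.1% |
| f = 1 | 0% | 0% | 0% |

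Both p and f are assumptions. If f is equal in the two arms, a true risk difference d is seen as (1 − f)d: it shrinks and does not change sign.

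**The case against.** The strongest reply is that the exclusion is narrow. Its exception keeps anything worse than expected for the subject, which is how marked treatment-accelerated decline should appear. The eligibility criteria strengthen this: subjects with LVEF or percent-predicted FVC below 35%, near-term respiratory risk, or an anticipated need for non-invasive ventilation within 12 months are excluded (Protocol 8.2). In the remaining group, many respiratory or cardiac admissions over a year could be called unexpected. Sites are blinded (Protocol 9.5), so inconsistent classification would mainly cost sensitivity and would not be expected to favour an arm. Addendum 4 gives the small sample and few observations as its reason for not completing the hospitalization analysis. With enrollment closed, a new definition cannot govern events already classified.

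Most of this stands and limits the point. It does not remove it: what is expected is still left to unguided judgment, and the two sections still lack a rule for a serious event attributed to progression. If admissions were few, a by-arm table is easy to produce.

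A reader might infer that such an admission is necessarily neither an AE nor an SAE. The inclusive wording in 13.2.1.1 does not support that. A reader might also infer that only deaths are protected, or that an admission set aside leaves no trace by arm. The separate infusion-related endpoints, and the listings and analyses named in step 3 of the working, contradict both.

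**Conclusion.** The point holds as a conflict in the text with a probable consequence of inconsistent capture. Protocol 13.2.1.1 and 13.2.1.2 contain no seriousness override, adjacent sentences point in different directions, and no remaining display counts a non-fatal admission set aside as expected progression outside the infusion-related endpoints.

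Each affected subject is worth about 10 percentage points of SAE incidence in an arm of about 10. The probabilities in the table rest on assumed admission risks and assumed shares set aside, and show scale only. The equal-dilution statement assumes that blinded sites set aside the same share in both arms. It would be tempting to conclude that serious events were lost in this trial, but nothing in the documents shows that any such event occurred. This is a worthwhile, inexpensive improvement to a primary safety endpoint; it is not evidence of concealed harm.

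**What to change.** 1. For any remaining follow-up, reconcile Protocol 13.2.1.1 with 13.2.1.2 by stating that the progression exclusion does not apply to an event meeting a seriousness criterion. Such events are recorded as SAEs, with DMD progression entered as the suspected cause where the investigator thinks so.
2. Have sites reconcile hospitalizations in source records against the SAE database before lock or, if lock has passed, as a documented post hoc check. Searching source records matters because an admission set aside as progression may never have reached the trial database.
3. Add to SAP 7 a by-arm listing and count of all-cause hospitalizations, with those attributed to DMD progression shown separately. This also partly restores the analysis that the Protocol Synopsis still promises in the safety population.

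With enrollment closed, the second and third steps matter more than the first. The cost is one sentence, one site query, one small table and perhaps a few additional SAE forms for events attributed to DMD.

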13.2.1.2. Serious Adverse Event (SAE)

An AE is considered “serious” if, in the view of either the Investigator or Capricor, it results in any of the following outcomes:

- Death
- Life-threatening adverse event
- Inpatient hospitalization or prolongation of existing hospitalization
- Persistent or significant incapacity or substantial disruption of the ability to conduct normal life functions
- Congenital anomaly/birth defect

Important medical events that may not result in death, be life-threatening, or require hospitalization may be considered serious when, based upon appropriate medical judgment, they may jeopardize the subject and may require medical or surgical intervention to prevent one of the outcomes listed in this definition.

Examples of such medical events include bronchospasm requiring intensive treatment in an emergency room or at home, blood dyscrasias, or convulsions that do not result in inpatient hospitalization, or the development of drug dependency or drug abuse.

Complications that occur during a hospitalization are AEs. When the hospitalization is prolonged due to the complication or the complication fulfills any other serious criteria, the event is reported as an SAE. Hospitalization for elective treatment of a pre-existing condition that did not worsen from baseline is not considered an SAE.

13.2.1.3. Expected Adverse Events

There is some risk of developing transient DSA with the CAP-1002 allogeneic product. All subjects will be monitored during the trial for immune sensitization as outlined in Table 3.

Other risks of the infusion procedure include those risks that are possible with the intravenous administration. These include risks related to infection, bleeding, pain, and bruising and/or hematoma at the vascular access site(s).

13.2.1.4. Unexpected Adverse Events

An AE is considered “unexpected” if it is not listed in the Investigator’s Brochure or is not listed at the specificity or severity that has been observed, if the Investigator’s Brochure is not required or available, or if it is not consistent with the risk information described in the general investigational plan or elsewhere in the current application.

“Unexpected,” as used in this definition, also refers to adverse events or suspected adverse reactions that are mentioned in the Investigator’s Brochure as occurring with a class of drugs or as anticipated from the pharmacological properties of the drug, but are not specifically mentioned as occurring with the particular drug under investigation.

Expedited reporting is required for serious unexpected AEs as discussed in Section [13.2.4](#).

13.2.1.5. Other Adverse Event (OAE)

OAEs will be identified by the Medical Monitor during the evaluation of safety data for the planned interim analysis and Clinical Study Report. Significant adverse events of particular clinical importance, other than SAEs and those AEs leading to discontinuation of the subject from the trial, will be classified as OAEs.

For each OAE, a narrative may be written and included in the Clinical Study Report.

13.2.2. Relationship to Investigational Product

The Investigator will assess the relationship (causality) of an AE to the investigational product and administration procedure.

Causality will be defined as follows:

- **Probable:** adverse events that, after careful medical evaluation, are considered with a high degree of certainty to be related to the investigational product or administration procedure. The following characteristics will apply:
 - A reasonable temporal relationship exists between the event and the investigational product or administration procedure, and
 - The event is a known reaction to the investigational product or administration procedure, which cannot be explained by an alternative etiology commonly occurring in the population/individual.
- **Possible:** adverse events that, after careful medical evaluation, do not meet the criteria for a probable relationship to the investigational product or administration procedure, but for which a connection has reasonable certainty. The following characteristics apply:
 - The event occurs after exposure to the investigational product or administration procedure, and

- The event is not a known reaction to the investigational product or administration procedure, but cannot be explained by a commonly occurring alternative etiology, or
 - In the absence of a temporal relationship, the event cannot reasonably be explained by an alternative etiology.
- ***Unlikely***: adverse events that, after careful medical evaluation, do not meet the criteria for possible or probable relationship to investigational product or administration procedure and for which a connection is unlikely. The following characteristics will apply:
 - The event does not follow a reasonable temporal sequence from administration of the investigational product or administration procedure, or
 - May be explained by commonly occurring alternative etiology in the population/individual, or
 - May have been produced by environmental factors, and there is no apparent pattern of response to the investigational product or administration procedure.

An adverse event will be reported as “related” when causality is evaluated by an Investigator as probably or possibly related to the investigational product and/or the administration procedure. Related adverse events indicate a potential cause-and-effect relationship between the investigational product and/or administration procedure and the occurrence of the adverse event.

An adverse event will be reported as “unrelated” when causality is evaluated by an Investigator as unlikely related to the investigational product and/or administration procedure by the Investigator. Unrelated adverse events indicate no relationship between the occurrence of the adverse event and the investigational product and/or administration procedure.

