7.2. Trial Endpoints

7.2.1. Primary Endpoints

The **primary safety endpoints** include the incidence of the following from baseline through the 12-month timepoint:

- Acute respiratory decompensation within 2 hours following IP administration
- Hypersensitivity reaction
 - Hypersensitivity reaction is defined as a clinical syndrome including, but not limited to, fever, leukocytosis, or rash with onset \leq 2 hours post infusion and lasting $<$ 24 hours, in the absence of clinical signs of concomitant infection.
- All-cause mortality
- Serious adverse events
- Treatment-emergent adverse events related to IP or administration procedure
- Immune sensitization syndrome
 - Immune sensitization syndrome shall be defined as: (a) clinical signs and symptoms consistent with systemic inflammation (e.g., fever, leukocytosis, rash or arthralgia) with onset \geq 24 hours post infusion and the absence of clinical signs of concomitant infection, **AND** (b) elevation of anti-human leukocyte antigen (HLA) antibodies against the donor cells (i.e., DSAs), detected \leq 30 days following onset of syndrome, of (i) \geq 2000 MFI if baseline MFI \leq 1000, or (ii) \geq 2 times baseline otherwise

The **primary efficacy endpoint** is change from baseline to the 12-month timepoint in functional capacity as assessed by the mid-level (elbow) dimension of the PUL 1.2.

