between the drug/biologic and the adverse event. Serious, unexpected suspected adverse reactions (SUSARs) are SAEs that are unexpected and are possibly or probably related to participation in the research. Expedited reporting is required for all SUSARs. Capricor will send an IND Safety Report to the FDA within 7 calendar days of receipt for fatal/life-threatening events, and within 15 calendar days of receipt for non-fatal/non-life-threatening events that qualify for expedited reporting.

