3.1. Adverse Events

This study utilized an independent Clinical Events Committee (CEC) to adjudicate all potential primary safety endpoints. The CEC data review was conducted in a blinded fashion and the results were provided only when the adjudication process yielded a different conclusion on the Treatment-Emergent Adverse Events (TEAE) as compared to the original TEAE assessment (i.e., the raw TEAE data). Since the adjudicated AE data set only contains the subset of adverse events which the adjudication committee reviewed, these data will be listed separately and not summarized due to their sparseness. In order to provide a comprehensive assessment of all TEAEs, the raw TEAE data will be reported in listings and summary tables for the safety population.

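### The causality scale has no related grade for an event with a plausible common alternative cause, so related TEAEs, a primary safety endpoint, can be under-counted

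*Protocol*

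**What the plan says.** Protocol 7.2.1 includes among the primary safety endpoints the incidence of "Treatment-emergent adverse events related to IP or administration procedure". Relatedness comes from Protocol 13.2.2, where "The Investigator will assess the relationship (causality) of an AE to the investigational product and administration procedure".

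The three grades in 13.2.2 are built as follows.

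- **Probable** requires "A reasonable temporal relationship exists between the event and the investigational product or administration procedure, and" and, in addition, a known reaction that no common alternative etiology can explain.
- **Possible** applies to events that miss Probable but where a connection is reasonably certain. The event must follow exposure and meet one of two descriptions. The first is "The event is not a known reaction to the investigational product or administration procedure, but cannot be explained by a commonly occurring alternative etiology, or". The second is "In the absence of a temporal relationship, the event cannot reasonably be explained by an alternative etiology".
- **Unlikely** applies to events that meet neither grade above and where a connection is thought unlikely. Its features are joined by 'or', and one is "May be explained by commonly occurring alternative etiology in the population/individual, or".

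Probable and Possible are reported as related. Unlikely is reported as unrelated, which the section takes to mean no relationship.

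Protocol 13.2.4 uses the same grades for expedited reporting: SUSARs "are SAEs that are unexpected and are possibly or probably related to participation in the research".

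SAP 7.1 bases all adverse event summary tables on TEAEs as adjudicated by the CEC. The later SAP Addendum, Section 3.1, lists the adjudicated data without summarizing them and says that "the raw TEAE data will be reported in listings and summary tables for the safety population".

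**The concern.** Infusion reactions such as fever or rash can look like ordinary intercurrent illness. For such an event an investigator will often see two candidate causes, the product and something common. A causality scale needs a grade for that case, and the middle grade is the natural place. Here the middle grade is closed to it, because an alternative explanation rules out Possible as firmly as it rules out Probable.

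The endpoint at stake is one of six primary safety endpoints in a 20-subject trial, so a few gradings matter. Any error has one direction: events with mixed causes leave the related count and none enter it. Because the wording gives no grade to an investigator who thinks a connection is not unlikely, two sites could also record the same event differently.

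**Working it through.** No figure in the documents depends on this point, and Protocol 14.4 says that safety endpoints carry no formal test. The check is therefore one of logic, followed by the size of one subject's contribution.

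**Step 1. Conditions.** For an event after exposure, let T = reasonable temporal relationship, K = known reaction, A = a common alternative etiology can explain it.

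- Probable: T and K and not A.
- Possible, first route: not K and not A.
- Possible, second route: not T and not A.
- Unlikely: neither of the above, and a connection judged unlikely.

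However the 'and' and 'or' under Possible are grouped, both routes contain not A.

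**Step 2. All eight combinations.**

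| T | K | A | Grade | Reported as |
|---|---|---|---|---|
| yes | yes | no | Probable | related |
| yes | no | no | Possible | related |
| no | yes | no | Possible | related |
| no | no | no | Possible | related |
| yes | yes | yes | neither related grade | unrelated, or no grade |
| yes | no | yes | neither related grade | unrelated, or no grade |
| no | yes | yes | neither related grade | unrelated, or no grade |
| no | no | yes | neither related grade | unrelated, or no grade |

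All four combinations without an alternative are related, and none of the four with an alternative is. On the literal criteria, relatedness is decided by A alone. An event with no temporal link and no other explanation counts as related, while a known reaction with close timing and a possible common cause does not.

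**Step 3. Where the fifth row goes.** If the investigator judges a connection unlikely, the event is Unlikely and reported as unrelated. If not, the Unlikely lead-in is not satisfied either and the event has no grade. SAP 4.3 counts missing relatedness as possible, so a blank entry would be counted as related while the same event graded Unlikely would not.

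**Step 4. Size.** Protocol 14.2 gives 20 randomized subjects and Protocol 7.4 gives 1:1 allocation. Arm sizes are not stated, so 20 / 2 = 10 per arm is an assumption. One subject whose only candidate related event is graded Unlikely changes that arm's incidence by 1/10 = 10 percentage points. With 8 per arm it is 1/8 = 12.5 points, and with 12 it is 1/12 = 8.3 points. How many subjects are affected is not in the documents, so the total under-count cannot be computed.

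**The case against.** The strongest reply is that 13.2.2 is a judgement scale. Each grade opens with careful medical evaluation, and Unlikely requires both that the event fails the other grades and that a connection is unlikely. This stands against two stronger readings that a reader might infer. First, the alternative-cause feature does not by itself force an event into Unlikely, because the lead-in must also be met. Second, Possible and Unlikely do not overlap for an untimed event with no alternative: the lead-in to Unlikely excludes anything that meets Possible. The reply does not supply a related grade for the mixed-cause event. It only replaces a wrong grade with no grade.

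Other endpoints catch part of the loss. Hypersensitivity reaction, acute respiratory decompensation, SAEs, deaths and immune sensitization syndrome do not use this scale, and the secondary safety endpoint covers all adverse events. The cover is incomplete. Under Protocol 7.2.1, hypersensitivity requires onset within 2 hours and immune sensitization requires onset at 24 hours or later plus an antibody rise. Both exclude events with clinical signs of concomitant infection. Among the primary safety endpoints, a non-serious reaction starting between those times can be counted only as a related TEAE, unless it is respiratory decompensation at the 2-hour limit.

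The CEC adjudicates potential primary safety endpoints, and with 20 subjects its listing can be read case by case. However, the documents give it no separate causality definition, and the Addendum's summary tables use the raw data.

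On expedited reporting, the concern is limited. Protocol 13.2.4 sends every SAE to the sponsor within 24 hours of discovery and separately applies a reasonable-possibility test for FDA reports.

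A reader might also infer from SAP 7.1 that the summary of events within 24 hours of infusion was dropped. That does not follow: Protocol 14.4.2 requires it, SAP Section 8 does not list it as removed, and the final table list is redacted.

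**Conclusion.** The point holds as a gap in a stated rule. Section 13.2.2 offers no related grade to any event with a plausible common alternative, including a known reaction with close timing. Related-TEAE incidence can be too low, and grading can differ between sites.

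The documents do not show that an under-count occurred, how large it was, or which arm it affects. That depends on how many events had a plausible alternative and on how literally investigators applied the criteria. The only size available is about 10 percentage points per reclassified subject, assuming about 10 per arm and no other related TEAE in that subject. The effect is confined to the related-TEAE endpoint and, more weakly, to SUSAR classification.

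**What to change.** Reconcile the grades in Protocol 13.2.2 so that each event has exactly one:

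- **Probable:** unchanged.
- **Possible:** does not meet Probable, has a reasonable temporal relationship, and no alternative etiology is clearly more likely than the product or procedure.
- **Unlikely:** all other events.

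Keep the existing route to Possible for events without a temporal relationship, as a second way to meet that grade. If it is removed, show the effect separately, because removal alone can lower the related count. With the route kept, no event now graded related becomes unrelated.

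For data already collected, first confirm that the CEC is still blinded; Protocol 9.5 guarantees this only until follow-up of the enrolled subjects ends. If it is, have the CEC re-rate TEAEs graded Unlikely with onset after an infusion, using the corrected wording. Report related-TEAE incidence by arm twice: as graded under the existing scale (primary), and under the corrected scale (labelled post hoc sensitivity). The label matters because Protocol 9.5 records that designated sponsor personnel have already seen treatment assignments and aggregate results.

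The cost is a wording change, a note to sites and a short CEC re-read of what should be a small list. Related-TEAE counts may rise.
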